14.0 Withdrawal of Subjects

The PI may withdraw a participant from the study at any time if they decide it is in their best interest, if they do not follow the investigator's instructions, or if they fail to keep study visits. This may also occur if there is a protocol violation or early closure of the study.

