The interprofessional team of investigators for this study includes a mentee ([name]) with a clinical background as a pediatric acute care nurse and research experience with exploring barriers in access to care among children with CCC. Mentors include an R01 funded nurse scientist who is an expert in intervention development and the conduct of clinical trials ([name]: primary mentor), an R01 funded clinical psychologist with extensive expertise in technology, user-based design, and intervention adaptation ([name]: co-mentor), a pediatric hematologist/oncologist specializing in clinical care and research with populations with SCD ([name]: co-mentor), and a biostatistician with extensive research experience ([name]: co-mentor). This complementary interdisciplinary team has the knowledge, skills, and access to the population to successfully conduct this study, but will also provide the mentee with mentorship and training experiences in theory-based, technology-enhanced intervention research among a population of children with a CCC and their caregivers.

The purpose of this second phase of this study is to conduct feasibility testing of an innovative, technology-based intervention to improve self-management behavior, quality of life, and symptom management (SMYLS) in a sample of children with SCD and their families. Three components are included in the intervention: previously tested educational materials for adults with SCD and their families, a publicly available mHealth application for tracking pain in SCD, and a model of patient-provider communication delivered via mHealth that has been tested with older children with SCD. The goal of the proposed research is to use the theory-based Pediatric Self-Management Model to tailor and pilot test the effect of an integrated intervention on psychosocial and physical symptom management and quality of life for children with SCD ages 8-17 years and their caregivers.

During this second phase of this study, we seek to achieve the following aims:

Primary aim of the study is to: Assess feasibility of implementation processes *including reach, enrollment, fidelity, adoption, acceptability, and satisfaction using the RE-AIM framework with process measures, surveys, and key informant interviews.*

Secondary Aim: Investigate the presence of signals of efficacy on measures of self-management, and physical and psychological symptoms and quality of life.

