SCD as a CCC based in health disparity. Because children with SCD and their families have high health care and “other” needs that endure throughout their lifetime, preventive actions are necessary in early childhood to avoid or mitigate adverse effects of the disease process. For optimal management and minimal adverse effects, persons with SCD and/or caregivers must coordinate appointments with various providers, continuously monitor symptoms, and obtain preventive home therapies. Often, challenges are pronounced early in the disease process as caregivers learn about the disease and treatments. Typically, a multidisciplinary team is established and caregivers learn to coordinate and maintain care. However, SCD primarily affects an underserved population (i.e., African Americans) who disproportionately face barriers such as transportation, obtaining childcare, and taking time from work. In fact, low-income children with SCD have significantly higher hospitalizations and ED visits than other children in general.⁹

Methods to enhance self-care of SCD by affected individual and the family are needed. Self-care interventions to prevent adverse effects of the disease process have not been well implemented for children with SCD. Fortunately, assistance with providing reliable sources of disease and treatment related information, decision-making, and communication with the care team via technology improve family-centered self-management behaviors in older children (ages 10-17 years) with SCD.¹⁰ Assisting families caring for an infant or young child with SCD via a similar technology-based model may lead to improved self-management and quality of life outcomes. Providing resources via this mechanism may reduce burden and maximize outreach to this difficult to reach, underserved, high needs population. Traditional barriers to care such as transportation, childcare, and work conflicts can be overcome. Long-term management of SCD and prevention of adverse outcomes also requires support for self-management skill development. Through technological resources and collaborative relationships with providers, caregivers can receive support to develop self-management skills.

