Demographics/clinical characteristics	Age, child age, health history, race/ethnicity, medications, health care utilization, rural/urban residence, insurance, caregiver demographics, family characteristics	Caregiver interview; baseline
Reach: Sample Recruitment	Monitoring of sample representativeness; types of recruitment activities; rates of recruitment; % eligible, consented, provided with informational session	Recruitment tracking forms; quality checks by PI; weekly meetings with mentor, clinic staff, and research team
Efficacy: Child (by proxy): Pain Fatigue Quality of life Caregiver: Fatigue Emotional distress: anxiety Emotional distress: depressive symptoms Measures of self-management behaviors: Monitoring and tracking symptoms Attending clinic appointments Administering home medications and treatments	PROMIS Parent Proxy: Pain Interference* ^{21,22} (age 5 and older) Self-efficacy SEMCD-6 PedsQL with Sickle Cell Disease Module (proxy = 0.97) ²³ (age 2 and older) PedsQL Multidimensional Fatigue Scale in Sickle Cell Disease (proxy = 0.95) ²⁴ (age 2 and older), PROMIS Fatigue SF, Depression SF (>0.9) ²⁵ PROMIS Emotional Distress: Anxiety (0.97) ²⁶ PROMIS Emotional Distress: Depressive symptoms SF (0.97) ²⁷ Daily pain severity rating; daily pain type rating # days recorded symptoms; # days and types of recorded treatments; # scheduled clinic appointments attended; # days daily mediation administered; # days PRN medications administered	Review and content analysis of transcriptions of text messages; review and content analysis of recorded teleconferences; tracking forms; fidelity checklist; transmissions from web-based application to nurse; post-intervention interviews; weekly meeting with mentor, clinic staff, and research team; baseline, mid-intervention, post-intervention, 3-months post-intervention

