Adoption: Adherence Acceptability Education	# days symptoms recorded; # times educational component accessed; length of time in minutes educational component accessed; # text messages and videoconferences with nurse Caregiver satisfaction; # problems reported; types of problems reported # times accessed educational materials; length of time in minutes educational materials accessed # days recorded symptoms; # contacts (text or videoconferencing) with nurse pertaining to symptoms	Tracking forms; content analysis from text messages and videoconferences with nurse, data transmitted from web-based application; fidelity checklist; weekly meetings with mentor and research team; caregiver interview at end of study

Symptom monitoring and tracking	# and type (screening, referring, coaching, supporting) of contacts (text or videoconferencing) with nurse	
Patient-provider communication	Collaborate for Parents	
Implementation: Technology	# problems encountered with mobile device, # problems reported to research staff; types of problems reported	Tracking forms; weekly meeting with mentor and research team; caregiver interview at end of study
Consistency of intervention	instructional session conducted as planned; fidelity to protocol maintained MAPS	
Maintenance: Projection of future adoption	# caregivers who would continue intervention; caregiver perception of the intervention; feasibility of nurse role	Caregiver interview at end of study; weekly meetings with mentor, clinic staff, and team

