4.0 Study Endpoints

Study end points include: Successful study completions, Consent withdrawals, PI terminations, Lost contact with the patient, and unexpected adverse events.

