Post-intervention interviews. All 30 caregivers and their children will be asked if they would like to participate in the 3-month post-intervention key informant interviews with the PI to obtain more in-depth data on accessibility, usability, and adherence to intervention. However, only a subset of 15 dyads will be chosen to participate. Selection will be by computer at random. Both caregiver and child will have to agree to participate in the interview to be eligible for selection. Dyads have a 50-50 chance of being randomly selected. Semi-structured interviews will be conducted using a qualitative descriptive approach,¹⁷ will last approximately 45-60 minutes, and will be conducted according to an interview guide with open-ended questions and prompts. These interviews will be recorded for later nVivo qualitative data analysis. Reimbursement for dyads will be a \$50 gift card provided at each of the 4 data collection points, with dyads in key informant interviews receiving an additional \$40 gift card. All payments will be given to the caregiver. Selected caregivers will be given the option of having the interview conducted in-person in a private room at MUSC or by telephone in the comfort and safety of their own home.

Measures. Children (8-17 years) and Caregivers will complete age-appropriate self-report assessments at baseline, mid-intervention (6 weeks), post-intervention (12 weeks), and 3 months post-intervention as previously described. Self-report and proxy assessments will be collected during meetings between the PI or PC and the participant. Depending on participants’ preference and availability visit 2, 3 and 4 surveys will be completed either by phone or electronically via REDCap survey or by paper and pencil. All data will be recorded in REDCap by the PC.

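### The PI's discretion to withdraw dyads for non-adherence or missed visits, when used, makes drop-out partly a PI decision, loses later data and can bias adherence in either direction

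*Combined protocol and SAP*

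**What the plan says.** The document holds two parallel protocols, for ages 8-17 and 0-7, each with 30 dyads. Section 14.0 is the same in both. The PI may withdraw a participant from the study in the participant's best interest, "if they do not follow the investigator's instructions, or if they fail to keep study visits", and also for a protocol violation or early closure. It gives no number of missed visits, level of non-use or timing, and it does not say whether any data are collected afterwards.

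The primary aim in Section 1.0 is to "Assess feasibility of implementation processes", including fidelity, adoption and acceptability. The RE-AIM measures table in Section 3.0 records adherence as usage counts: "days symptoms recorded; # times educational component accessed; length of time in minutes educational component accessed". Under self-management behaviours it also counts "scheduled clinic appointments attended". Section 4.0 lists as endpoints "Successful study completions, Consent withdrawals, PI terminations, Lost contact with the patient, and unexpected adverse events". Section 12.0 treats drop-out as a feasibility proportion. It also plans to compare the demographic and clinical characteristics of adherers, whom it equates with completers, against non-adherers and drop-outs taken together.

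Section 10.0 already allows remote follow-up: "visit 2, 3 and 4 surveys will be completed either by phone or electronically via REDCap survey or by paper and pencil".

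**The concern.** In most trials a clause like this is routine. Here it acts on what the study sets out to observe. Under Section 10.0 the PI or coordinator instructs participants on using the device and the intervention. Under Section 13.0 the PI or coordinator reviews participant logs for compliance. The PI can therefore see low use and end that dyad's participation. A dyad that does not take up the app is a feasibility finding. Once withdrawn, it becomes a PI termination with no stated route to the 6-week, 12-week or 3-month surveys, or to the end-of-study interviews that inform acceptability, implementation and maintenance.

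At stake are the drop-out rate, the adherence summaries, the pre-post change estimates, and the accounts of the families best placed to explain why the app did not suit them. Section 2.0 says the affected population "disproportionately face barriers such as transportation, obtaining childcare, and taking time from work", so missed visits are foreseeable in this sample.

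**Working it through.** **Inputs from the documents.** 30 dyads per protocol (Section 6.0); stated precision of ±0.11 to ±0.16 for feasibility proportions of 0.10 to 0.30, and drop-out of up to 30% for the impact measures (Section 12.0); 12 weeks of app use, or 12 × 7 = 84 days (Section 10.0). The documents give no adherence threshold, denominator, analysis set or missing-data rule.

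**Step 1: the plan's own figure.** The half-width is 1.96 × √(p(1−p)/n), taking 95% confidence, which the plan states for the impact measures only.
- n = 30: 1.96 × √(0.09/30) = 0.107 and 1.96 × √(0.21/30) = 0.164, which match the stated 0.11 and 0.16.
- n = 21 (after 30% drop-out): 1.96 × √(0.09/21) = 0.128 and 1.96 × √(0.21/21) = 0.196, which do not match.

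The sample-size text therefore counts feasibility proportions over all 30. It does not say that the analysis will.

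**Step 2: drop-out.** Each PI withdrawal of a dyad that would otherwise have stayed adds 1/30 = 0.033. With 3 voluntary losses (assumed):
- no PI withdrawals: 3/30 = 0.10
- 3 PI withdrawals: 6/30 = 0.20
- 6 PI withdrawals: 9/30 = 0.30, the plan's upper limit

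These are upper bounds, because some of those dyads might have left anyway.

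**Step 3: adherence as a proportion.** The plan sets no threshold, so the counts are assumed. Compare A/30 with A/(30 − k), where A dyads are adherent and k non-adherent dyads are withdrawn.

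| Adherent | Withdrawn | Over all 30 | Over retained | Shift |
|---|---|---|---|---|
| 18 | 6 of 12 | 18/30 = 0.60 | 18/24 = 0.75 | 0.15 |
| 21 | 6 of 9 | 21/30 = 0.70 | 21/24 = 0.875 | 0.175 |
| 24 | 2 of 6 | 24/30 = 0.80 | 24/28 = 0.857 | 0.057 |
| 27 | 1 of 3 | 27/30 = 0.90 | 27/29 = 0.931 | 0.031 |

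Over all 30 the shift is zero. Over retained dyads it ranges from small to larger than the plan's ±0.16.

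**Step 4: adherence as a usage count, which is how Section 3.0 measures it.** Assume 18 dyads record symptoms on 70% of days (58.8 of 84) and 12 on 20% (16.8 of 84), and that 6 of the 12 are withdrawn at week 6.
- No withdrawals: (18 × 58.8 + 12 × 16.8)/30 = 42.0 days.
- Retained only: (18 × 58.8 + 6 × 16.8)/24 = 48.3 days, biased upward.
- All 30, with counts cut off at withdrawal: each withdrawn dyad loses 0.20 × 42 = 8.4 days, so 42.0 − (6 × 8.4)/30 = 40.3 days, biased downward.

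**Step 5: pre-post change.** If 6 withdrawn dyads would have had a mean change differing by D from the other 24, leaving them out shifts the mean by (6/30) × D = 0.2 × D. The documents give neither the size nor the sign of D.

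**The case against.** The strongest reply is that a reader might infer from Section 14.0 that adherence results are biased upward, and the documents do not support that. The clause is permissive, so leaving a non-adherent dyad enrolled also complies with it. The plan never adopts a retained-only denominator: Step 1 points to 30, and the Section 12.0 comparison puts withdrawn dyads with those who did not adhere. Step 4 shows that the bias can run downward. All of this stands.

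Section 4.0 also lists PI terminations apart from consent withdrawals and lost contact, so a reader of the results could separate them from voluntary exit. That stands for counting. It does not recover surveys, logs or interviews that were never collected, and Section 12.0 does not say whether PI terminations enter the drop-out rate. The planned comparison of completers with others covers baseline characteristics, not outcomes.

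Study-visit attendance is not itself a listed RE-AIM measure; the table counts clinic appointments. The investigator's instructions are not defined as app use either. Both are fair limits, but study completion is an endpoint, and instructions on using the app are among those the protocol says are given.

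Finally, retention texts at weeks 3, 9, 15, 18 and 21 and the remote survey routes already ease the barriers that families face, and nothing shows that any particular group would be withdrawn. That is correct. The same remote routes also mean that a missed visit need not end data collection.

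**Conclusion.** The concern holds in a conditional form. If the PI uses the discretion, drop-out becomes partly a PI decision. Because the plan provides for no data collection after withdrawal, later information from the least engaged families is lost. The effect on adherence depends on a summary rule that the plan does not state: upward over retained dyads, downward for truncated counts over all 30, and none for a proportion over all 30. The sizes in the working rest on assumed numbers of non-adherent and withdrawn dyads. They show that a handful of withdrawals can move a result by as much as the plan's own precision, not that this will happen.

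A reader might also infer that the pre-post changes will look too favourable because families for whom the app failed were removed. Selection is plausible, but its direction is not established. The plan sets no progression threshold, so no stated decision turns on the figure. The point still merits correction before the clause is used, because it reaches the primary aim and data not collected cannot be recovered later.

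**What to change.** In Section 14.0 of both protocols:
- Remove not following instructions and missing study visits as grounds for withdrawal from the study.
- State that the protocol-violation ground does not cover app non-use or missed visits; otherwise non-adherence could re-enter through it.
- Leave the best-interest and early-closure grounds unchanged.
- State that a dyad that stops using the app or misses a visit stays enrolled, is offered the remaining surveys and interviews by the phone or REDCap routes already allowed, and has its app log kept.

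In Section 12.0 of both protocols, state that adherence and completion are reported over all enrolled dyads, and that PI terminations are shown separately from voluntary drop-out, in line with Section 4.0.

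The cost is a wording amendment and a few more reminders through existing channels. Reported adherence may be lower than it would be among retained dyads alone.

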15.0 Risks to Subjects

Based on Phase I of the study, we do not anticipate any significant risks related to the completion of the surveys and key informant interviews in this study. However, as with any research study there is a risk of disclosure of information that can lead to a loss of confidentiality. As well as having a comprehensive DSMP that details data safety, handling, monitoring, storage and security procedures, we will further minimize the potential for loss of confidentiality through the physical separation of participant names from their research record.

Additionally, it is possible that a participant might experience some emotional distress while responding to the survey questions or participating in key informant interviews. If this were to occur, the participant would be referred to a psychologist or psychiatrist for counseling. Reactions will be monitored by the PI (who will be conducting the interviews) and signs of significant distress will be followed-up to identify any serious psychological problems. In the rare and unexpected event of serious or life threatening level of distress, a psychologist or psychiatrist will be contacted as well as the participant's primary care provider of record.

1.0 Objectives / Specific Aims

Specific Aims: Few family-centered self-management interventions exist to assist children with sickle cell disease (SCD) and their families, which deprive this population of skills that may improve symptom management and quality of life. SCD is an inherited complex chronic condition (CCC) that leads to adverse health outcomes such as pain and organ damage affecting approximately 100,000 people in the US. In addition to living with pain and negative health outcomes, children and adults with SCD also face disparities in access to care. Infants and young children with more complicated CCCs, such as SCD, and those who have fewer resources are at greater risk for adverse outcomes such as increased hospital and emergency department (ED) utilization and physical and psychosocial morbidity. Children with SCD and their families, particularly those who are underserved, would benefit from interventions designed to bolster self-management skills and enhance preventive management of the disease to reduce negative complications. Importantly, caregivers of young children with SCD are often new to the disease process and have unique needs and challenges.

Interventions designed to address the unique needs of and barriers encountered by this population could improve effective management of the disease in the home setting. In addition, technology-based resources such as mobile health applications for symptom tracking, may allow intervention delivery to typically difficult-to-reach populations, thereby reducing access barriers to care, including lack of transportation and obtaining childcare. Further, incorporating theory-based family-centered self-management strategies is crucial to support families in developing sustainable, improved self-management behaviors (e.g. monitoring symptoms, and attending clinic appointments) which will ultimately improve symptom management (e.g. pain, fatigue) and quality of life, and decrease costly emergency department (ED) visits and hospitalizations.

The interprofessional team of investigators for this study includes a mentee ([name]) with a clinical background as a pediatric acute care nurse and research experience with exploring barriers in access to care among children with CCC. Mentors include an R01 funded nurse scientist who is an expert in intervention development and the conduct of clinical trials ([name]: primary mentor), an R01 funded clinical psychologist with extensive expertise in technology, user-based design, and intervention adaptation ([name]: co-mentor), a pediatric hematologist/oncologist specializing in clinical care and research with populations with SCD ([name]: co-mentor), and a biostatistician with extensive research experience ([name]: co-mentor). This complementary interdisciplinary team has the knowledge, skills, and access to the population to successfully conduct this study, but will also provide the mentee with mentorship and training experiences in theory-based, technology-enhanced intervention research among a population of children with a CCC and their caregivers.

There are three main components within the study intervention: previously tested educational materials for adults with SCD and their families, a publicly available mHealth application for tracking pain in SCD, and a model of patient-provider communication delivered via mHealth that has been tested with older children with SCD. The goal of the proposed research is to use the theory-based Pediatric Self-Management Model to tailor and pilot test the effect of an integrated intervention on psychosocial and physical symptom management and quality of life for children with SCD ages 0-7 years and their caregivers.

During Phase I of this study, we refined the development and design of the intervention under study, by conducting user focus groups and pilot testing the app with provider feedback among a target population of end-users. Now, in Phase II, we aim to deploy the intervention in a real-world setting. The purpose of this second phase of this study is to conduct feasibility testing of an innovative, technology-based intervention to improve self-management behavior, quality of life, and symptom management in a sample of children with SCD and their families.

During this second phase of this study, we seek to achieve the following aims:

Primary Aim: *Assess feasibility of implementation processes including reach, enrollment, fidelity, adoption, acceptability, and satisfaction using the RE-AIM framework with process measures, surveys, and key informant interviews.*

Secondary Aim: *Investigate the presence of signals of efficacy on measures of self-management, and physical and psychological symptoms and quality of life.*

